3.4 Duration of the study participation

The study duration consists of the following periods:

Screening Period: 28 days

Treatment Period: All patients will receive a continuous 28-day treatment cycle of ASLAN003 until disease relapse, treatment failure (defined as failure to achieve a PR or higher within 4 cycles) unacceptable toxicity, withdrawal of consent or death.

Follow-up Period: All patients will be required to complete a safety follow-up visit within 28 days after the last dose of study treatment. All patients achieving CR or CRi will be followed for survival every 12 weeks post end of treatment (EOT) until disease relapse or death (in the absence of disease relapse) to find out the RFS.

Visit Schedule: In order to address the primary objectives of the study, if treatment is interrupted for any reason, it is important that all planned safety and efficacy assessments are performed at the scheduled time, regardless of whether the patient is receiving study treatment, or not, at the time.

The planned duration of entire study (treatment and follow-up) is approximately 2 years.

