3.1.1 Overall Complete Remission Rate

Overall complete remission rate (OCRR) is a co-primary endpoint in Part 1 and the primary endpoint in Part 2. It will be derived programmatically from the BM aspiration and peripheral blood results based on the IWG Criteria¹⁶ for AML (Cheson, 2003) as described below.

For patients without sufficient archival BM sample, BM aspiration will be performed during Screening. All patients will receive bone marrow aspiration for efficacy assessment on Day 1 of Cycle 2, 3, 4, 5 and will be repeated every 3 cycles after Cycle 5. Patients who've already achieved CR could omit the bone marrow aspiration at subsequent visits if there is a normal complete blood count with differential of the peripheral blood. Investigator may perform more frequent exam if required based on clinical judgment.

BM aspiration smears will be processed locally.

Following treatment discontinuation, patients who have achieved a CR or CRi, will continue to be followed up for every 12 weeks to assess the relapse free survival. For patients who have not achieved a CR or CRi during treatment, no further follow-up is required following treatment discontinuation.

These criteria categorize the visit response into the following response classifications:

- *CR with incomplete recovery of neutrophils and platelets (CRi):*

Achievement of CRi requires patients to satisfy all of the following:

- A disappearance of blasts in the peripheral blood.
- A decrease in BM blasts to <5% total BM nucleated cells demonstrated in BM aspirate.
- Absence of Auer rods
- No persistent extramedullary leukaemia

- *Complete Remission:*

Patient satisfies all of the criteria above and in addition has:

- Recovery of Neutrophils to $\geq 1.0 \times 10^9/L$ and Platelets to $\geq 100 \times 10^9/L$
- Transfusion-independence

- *Partial Remission:*

A PR is defined as recovery of neutrophils to $\geq 1.0 \times 10^9/L$ and Platelets to $\geq 100 \times 10^9/L$ and either:

- If the pre-treatment bone marrow blast percentage was 50% to 100%, the percentage of blast must decrease to a value between 5% and 25%
- If the pre-treatment BM blast percentage was 20% to less than 49%, they must decrease by at least half to a value of more than 5%

- A reduction in BM blast cells to <5% but with persistence of Auer rods.

- *Treatment failure:*

Failure to meet the criteria for CR, CRi or PR after 4 cycles of treatment will result in a best response of treatment failure.

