For the evaluation of OCRR, a binary variable will be created to indicate complete response status of each patient (complete responder or non-responder) defined as follows:

A patient will be classified as a complete responder if either of the following are achieved during the study and prior to starting subsequent AML treatment:

- Achievement of CR
- Achievement of CRi

Patients who do not satisfy the OCRR criteria outlined above (including patients with PR, treatment failure and any patients without evaluable post-treatment assessments) will be classified as non-responders for the assessment of OCRR.

Best response status will also be assessed. A patient's best response is defined as the best AML visit response observed, ranked in the following order:

CR > CRi > PR > Treatment failure.

OCRR is defined as the number (%) of patients with a best response of complete remission (CR) or complete remission with incomplete hematologic recovery (CRi), defined in accordance with the International Working Group (IWG) Response Criteria in AML.

All efficacy data collected, whether based on scheduled or unscheduled visits, will be included in the assessment of OCRR, with the exception of data collected following the start of subsequent AML therapy, which will not be included in the assessment of OCRR.

In all study parts, the primary analysis of OCRR will be assessed based on the evaluable for response (EFR) set with a sensitivity analysis based on the full analysis set (FAS).

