3.1.3 Clinical Benefit Rate

Clinical benefit rate (CBR) is a secondary endpoint in Parts 1 and 2.

CBR is defined as the number (%) of patients with an AML IWG best response of CR, CRi or partial remission (PR). Data obtained up until progression, or last evaluable assessment in the absence of progression, will be included in the assessment of CBR. This will be irrespective of whether or not patients discontinued treatment or received a subsequent therapy prior to progression.

All efficacy data collected, whether based on scheduled or unscheduled visits, will be included in the assessment of CBR, with the exception of data collected following the start of subsequent AML therapy, which will not be included in the assessment of OCRR.

In all study parts, the primary analysis of CBR will be assessed based on the evaluable for response (EFR) set with a sensitivity analysis based on the full analysis set (FAS).

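### Gaps in the PR rule (exactly 5% marrow blasts, baselines of 49 to <50%, and silence on residual disease) can turn a marrow response into treatment failure in CBR (minor; OCRR classification unchanged)

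*SAP*

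**What the plan says.** SAP 3.1.1 sorts each visit into a response category. Protocol 6.2 carries the same definitions.

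- **CRi** requires marrow blasts below 5%, no Auer rods, "A disappearance of blasts in the peripheral blood" and "No persistent extramedullary leukaemia". **CR** adds count recovery and transfusion independence.
- **PR** requires neutrophils of at least 1.0 and platelets of at least 100 (×10⁹/L), plus one of three marrow conditions, called routes here:
  - Route 1: baseline 50–100%, now in the 5–25% range.
  - Route 2: baseline from 20% to less than 49%; blasts have a two-part condition, "they must decrease by at least half to a value of more than 5" per cent.
  - Route 3: "A reduction in BM blast cells to <5% but with persistence of Auer rods".
- No PR route mentions blood blasts or extramedullary disease.
- The default is: "Failure to meet the criteria for CR, CRi or PR after 4 cycles of treatment will result in a best response of treatment failure". Protocol 3.4 makes the same event a reason to end treatment: "treatment failure (defined as failure to achieve a PR or higher within 4 cycles").

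Across visits, "best response is defined as the best AML visit response observed, ranked in the following order": CR, CRi, PR, treatment failure. SAP 3.1.3 then says "CBR is defined as the number (%) of patients with an AML IWG best response of CR, CRi or partial remission (PR"). SAP 7.3 reports CBR in Part 2 with two-sided 80% Clopper-Pearson intervals.

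**The concern.** A response classification should give every assessable visit a category. With everything else equal, a lower marrow blast percentage should not give a worse one. The PR text fails the first test in two places: at exactly 5% blasts, and at baselines between 49% and 50%. Read literally, it also fails the second test when there is residual disease outside the marrow.

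A patient caught in a gap, with no better visit, is scored as a treatment failure by default. That patient leaves the CBR numerator, has no listed time to response (SAP 3.1.5 counts CR, CRi or PR) and meets the four-cycle failure rule, which bears on continued dosing.

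**Working it through.** The plan states no figure to reproduce, so the check applies the written rules. Inputs are the SAP 3.1.1 criteria, with counts recovered throughout and the 5–25% range read as including 5%.

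**Step 1. Exactly 5%.** Take a patient with clear blood, no Auer rods and no extramedullary disease.

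| Baseline | Now | CR/CRi (<5%) | Route 1 | Route 2 | Route 3 | Result |
|---|---|---|---|---|---|---|
| 40% | 6% | no | no (baseline) | yes: 6 ≤ 20 and 6 > 5 | no | PR |
| 40% | 5% | no | no (baseline) | no: 5 is not above 5 | no | none |
| 40% | 4.9% | yes | – | – | – | CR or CRi |
| 60% | 5% | no | yes | – | no | PR |

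At 5% from a baseline of 40%, the result is also none in all 8 combinations of Auer rods, blood blasts and extramedullary disease (each present or absent). The marrow thresholds alone rule out every category.

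**Step 2. Baseline 49 to <50%.** For a fall to 10%:

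- Baseline 48%: route 2 applies (10 ≤ 24 and 10 > 5), so PR.
- Baseline 49.5%: route 1 needs 50% or more and route 2 needs less than 49%, so none.
- Baseline 50%: route 1 applies, so PR.

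At a baseline of 49 to <50%, the only PR route left is route 3, below 5% with Auer rods.

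**Step 3. Residual disease.** Take a baseline of 40% or 60% with blood blasts or extramedullary disease present.

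| Now | Auer rods | CRi | PR | Result |
|---|---|---|---|---|
| 10% | absent | no | yes (route 1 or 2) | PR |
| 3% | absent | no (residual disease) | no (route 3 needs Auer rods) | none |
| 3% | present | no | yes (route 3) | PR |

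The drop from PR at 10% to none at 3% occurs in 3 of the 8 combinations: no Auer rods, with blood blasts, extramedullary disease or both. This counts combinations of the rule's conditions and is not a probability.

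**Step 4. Size in CBR.** One affected patient with no other qualifying visit removes:

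- 1/20 = 5 points in Part 2, if all 20 patients are in the evaluable-for-response set;
- 1/6 = 16.7 points in a Part 1 cohort.

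As an illustration, 4/20 = 20% (80% interval 9.0–36.1%) becomes 3/20 = 15% (5.6–30.4%).

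**Step 5. OCRR.** SAP 3.1.1 counts PR and treatment failure both as non-response, so moving a patient between them changes OCRR by 0.

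**Step 6. Route 2 edited to a baseline of 20 to <50%, at least halved, to 5% or more.**

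- Baseline 40%, now 5%: 5 ≤ 20 and 5 ≥ 5, so PR.
- Baseline 49.5%, now 10%: 10 ≤ 24.75 and 10 ≥ 5, so PR.
- The step 3 result is unchanged, so it needs its own decision.

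**The case against.** The strongest reply concerns step 3. The inversion exists only if PR at 10% tolerates blood blasts and extramedullary disease, and the text never says that it does; it is merely silent. The SAP evaluates efficacy according to the cited IWG criteria. If the CRi exclusions were meant to carry over to PR, then 10% and 3% would both be non-PR and the inversion would disappear. This stands in part. SAP 3.1.1 applies the criteria as it sets them out itself, so the literal reading is the working one, but the sponsor's intention cannot be read from the documents. A reader might infer that residual disease was meant to be compatible with PR, and so that route 3 should simply be widened. The documents do not support that inference any more than its opposite.

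Second, best response is kept. A reader might infer that a patient seen at 10% and later at 3% loses PR in the analysis. That is not so: the earlier PR remains the best response. CBR changes only for a patient with no CR, CRi or PR visit at all.

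Third, Protocol 4.3 allows drug to be stopped when a patient no longer meets PR. It might be inferred that a further marrow fall forces a stop. That clause is permissive and most naturally means loss of response.

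Fourth, investigators might use judgement. SAP 9.2 does list an investigator's assessment beside the derived response. However, CBR is built on best response, which SAP 3.1.1 builds from these visit categories.

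None of these replies reaches steps 1 and 2, which need no view on residual disease.

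**Conclusion.** The main defect is in route 2, which is wrong as written at both ends. Its lower limit leaves exactly 5% without a category, while route 1 accepts 5% (on the inclusive reading). Its upper baseline limit does not meet the start of route 1. The secondary defect is an unstated rule on residual disease, which read literally ranks 3% below 10%.

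The effect is 5 points of CBR per affected patient in Part 2 and 16.7 points in a Part 1 cohort of 6. The documents give no frequency, so no expected effect can be stated. If marrow blasts are recorded as whole percentages, which is an assumption, 5% is an ordinary value and the baseline gap is the single value 49%. The residual-disease state needs several findings together and is probably rare.

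A reader might infer that the primary endpoint is biased. The classification rule gives no support for that, because OCRR treats PR and failure alike. An indirect path, in which a patient is stopped as a failure before a later CR or CRi, is conceivable, but nothing in the documents sizes it. CBR is secondary and descriptive and the study is not formally powered, so the point is minor.

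**What to change.** In SAP 3.1.1 and Protocol 6.2:

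1. **Route 2.** Change the baseline band to 20% to less than 50%, and require blasts to be at least halved to a value of 5% or more. State that the 5–25% range in route 1 includes its end points.
2. **Residual disease.** Before response data are reviewed, state one rule for all marrow levels. Either blood blasts or extramedullary disease also allow PR below 5%, or they preclude PR on all three routes. This is a clinical choice for the sponsor, and the documents give no ground for a default.

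The cost is two short edits in each document and the matching programming conditions. Edit 1 can only add PRs, at exactly 5% and at baselines of 49 to <50%, so CBR can only stay the same or rise. Under edit 2, CBR may rise if residual disease allows PR, or fall if it precludes PR. Baselines below 20% still have no PR route at 5% or above; these edits do not address that.

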3.1.2 Relapse-Free Survival

Relapse-free survival (RFS) is a secondary endpoint in Parts 1 and 2 and is defined for the sub-group of patients classified as responders for OCRR.

RFS is defined as the time the criteria for remission (CR or CRi) are first met until there is evidence of patient relapse, regardless of whether the patient is still taking study drug or has started other anti-AML treatment prior to relapse. (Note, the onset of the CR/CRi must have been before the start of subsequent anti-AML treatment to be classified as a responder for OCRR). Relapse is defined as:

- The reappearance of leukemic blasts in the peripheral blood or >5% blasts in the bone marrow not attributable to any other cause
- The appearance of new dysplastic changes
- The reappearance of or development of cytologically proven extramedullary disease
- The reappearance of a cytogenetic or molecular abnormality
- Death by any cause

In the event that the blood and bone marrow response assessments for a visit are performed on different dates, RFS will be calculated using the earliest date at which a relapse was detected. For example, if both the peripheral blood and bone marrow were assessed and both found to be indicative of relapse, RFS will use the earlier of the two assessment dates. However, if both were assessed, but only the marrow was found to be indicative of relapse, the date of the marrow assessment would be used as the date of relapse.

As described above, patients who die without evidence of relapse will be considered to have relapsed at the date of death, provided that the death does not occur following two or more missed assessments (up to 56 days following previous assessment). If the death occurs more than 56 days following the previous response assessment, the patient will be censored for RFS at the date of the last efficacy assessment in which they were alive and relapse-free.

Similarly, patients who are determined to have met the criteria for relapse more than 56 days after the last efficacy assessment will also be censored for RFS at the date of the last efficacy assessment in which they relapse-free.

For the purpose of evaluating whether RFS should be censored due to missed visits, a patient will be considered to have missed two assessments if neither the peripheral blood or bone marrow have been assessed for >56 days.

In all study parts, the primary analysis of RFS will be assessed based on the EFR set with a sensitivity analysis based on the FAS.

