4.3 Patient Withdrawal and Replacement

Patients may withdraw from any part of the study at any time without penalty and for any reason without prejudice to his or her future medical care. The Investigator will advise the Sponsor of the withdrawal of any patient.

Patients must be withdrawn from study drug under the following circumstances:

- Patient voluntarily withdraws from study participation;
- Disease recurrence;
- Ineffective treatment;
- Unacceptable toxicity;
- Patient's withdrawal of consent;
- Death;
- Pregnancy (refer to section 6.3.1.11)
- Significant protocol deviation;
- Lost to follow-up;
- If deemed by the Investigator that it is not in the patient's interest to continue with the study.

Withdraws from study participation (follow-up permitted):

Patients withdrawing from the study drug will be encouraged where possible to return to the site for a study follow-up visit, in particular for safety evaluations, study assessments and survival follow-up.

Disease recurrence:

Sites should continue to perform efficacy assessments for patients achieving CR or CRi until disease recurrence (or death in the absence of recurrence) in accordance with IWG criteria for AML. Patients will be withdrawn from the treatment if there is evidence of disease recurrence as defined by IWG Criteria¹⁶ (Cheson, 2003).

Ineffective treatment:

The study drug may be discontinued in the event of:

- Treatment failure (in patients who do not achieve a PR or above after 4 cycles of treatment)
- Relapse, as defined by the IWG Response criteria (for patients with a CR or CRi)
- No longer meeting the criteria for a PR (in patients who were previously determined to have a PR)

Once ineffective treatment has been established, as described above, no further efficacy assessments are required.

Unacceptable toxicity:

If the symptoms are not controlled with standard treatments and are considered to be clinically significant, study drug will be stopped and the patient will be withdrawn from the study drug. Patients removed from study drug for unacceptable toxicity will be followed until resolution or stabilization of the AE.

Patients with a response (CR or CRi) withdrawn from the treatment prior to disease relapse should continue to be followed until the relapse in accordance with the study plan.

Consent Withdrawal:

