Failure to meet the criteria for CR, CRi or PR after 4 cycles of treatment will result in a best response of treatment failure.

For the evaluation of OCRR, a binary variable will be created to indicate complete response status of each patient (complete responder or non-responder) defined as follows:

A patient will be classified as a complete responder if either of the following are achieved during the study:

- Achievement of CR
- Achievement of CRi

Patients who do not satisfy the CR criteria outlined above (including patients with PR, treatment failure and any patients without evaluable post-treatment assessments) will be classified as non-responders for the assessment of OCRR.

Best response status will also be assessed. A patient's best response is defined as the best AML visit response observed, ranked in the following order:

CR > CRi > PR > Treatment failure.

Based on the above definitions, the following efficacy endpoints will be evaluated:

Overall Complete Remission Rate: Defined as the proportion of patients with a best response of CR or CRi, defined in accordance with the IWG Response Criteria in AML, and described above.

Relapse Free Survival: Defined as the time the criteria for remission (CR or CRi) are first met until there is evidence of patient relapse or death from any cause (whichever happens first), regardless of whether the patient is still taking study drug.

Relapse is defined as:

- The reappearance of leukemic blasts in the peripheral blood or > 5% blasts in the BM not attributable to any other cause
- The appearance of new dysplastic changes
- The reappearance of or development of cytologically proven extramedullary disease
- The reappearance of a cytogenetic or molecular abnormality

Clinical Benefit Rate: Defined as the proportion of patients with an AML IWG best response of CR, CRi or PR.

The percentage change from baseline in BM blasts and peripheral blood blasts at Day 29 will also be evaluated.

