7.2.5 Survival Follow-up (± 7 days)

Survival follow-up by either telephone or clinic visit will be performed in patients achieving CR or CRi every 12 weeks post EOT until disease relapse or death (in the absence of disease relapse) to enable the assessment of RFS.

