3. ENDPOINTS

3.1 Efficacy Endpoints

Efficacy will be evaluated in accordance with the IWG Criteria¹⁶ for AML (Cheson, 2003). Definitions of the primary and secondary efficacy variables are described in Sections 3.1.1 to 3.1.6. In addition, the following principles will be applied:

For the evaluation of OCRR, TTR and TTCR, if bone marrow and peripheral blood assessments are both performed, the assessment date used will be the date of the bone marrow assessment. If only blood assessments are performed, the assessment date will be the date of the blood assessment.

For RFS, the date of relapse will be the assessment date of the first component that fulfills the criteria for relapse (Section 3.1.2). For example, if both the peripheral blood and bone marrow were indicative of relapse, but the blood assessment was performed first, then the date of relapse would be the date of the peripheral blood assessment. Similarly, if relapse was first detected due to the development of cytologically proven extramedullary disease, the date of detection for the extramedullary disease would be the date of relapse, even if the bone marrow and peripheral blood assessments were not performed until a later date.

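### The SAP's 56-day missed-assessment rule for RFS is shorter than every permitted off-treatment follow-up interval, so relapses found at a 12-week visit are censored even when no visit was missed

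*SAP*

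**What the plan says.** SAP 3.1.2 defines RFS for CR/CRi patients whether or not they are still on study drug, and includes death from any cause. It then adds a missed-assessment rule. A death counts "provided that the death does not occur following two or more missed assessments (up to 56 days following previous assessment"). Relapses get the same treatment: "patients who are determined to have met the criteria for relapse more than 56 days after the last efficacy assessment will also be censored" at the last relapse-free assessment. Two assessments are taken as missed "if neither the peripheral blood or bone marrow have been assessed for >56 days". There is no separate limit for the period after treatment.

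The off-treatment schedule is longer. Under SAP 3.1.1, patients with CR or CRi "will continue to be followed up for every 12 weeks to assess the relapse free survival". Protocol 7.2.5 says "Survival follow-up by either telephone or clinic visit will be performed in patients achieving CR or CRi every 12 weeks post EOT", with a ±7-day window. Protocol 4.3 says responders "withdrawn from the treatment prior to disease relapse should continue to be followed until the relapse". SAP 3.1 fixes the date: "the date of relapse will be the assessment date of the first component that fulfills the criteria for relapse".

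RFS is listed in both parts. It is summarised by Kaplan-Meier in Part 2 only, if there are enough events (SAP 7.2).

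**The concern.** A missed-assessment rule is meant for patients who were not seen when they should have been. Here one fixed limit, matched to the treatment cycle, is applied to a follow-up period whose planned interval is half as long again (84 against 56 days). A patient who attends everything is classed as having missed two assessments.

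Two kinds of event are lost: a relapse whose first positive test is at a scheduled off-treatment visit, and an off-treatment death more than 56 days after the last blood or marrow test. Each becomes a censoring at an earlier date. Because the event itself triggers the censoring, the censoring is informative, which violates the assumption behind the Kaplan-Meier estimate. The trial follows these patients in order to observe these events, and the analysis then discards them.

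**Working it through.** **The SAP's figure.** Cycles are 28 days, with hematology on Day 1 of each (Protocol Table 1 and 7.2.2.6). 2 × 28 = 56, which reproduces the limit. It spans two intervals, which is one skipped visit: 52 to 60 days with ±2-day windows.

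**On treatment.** Consecutive Day 1 visits are 28 ± 4 = 24 to 32 days apart, so attending patients never reach 56. Marrow every 12 weeks after Cycle 5 does no harm, because a blood count alone restarts the clock.

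**Off treatment.** The last scheduled hematology is at EOT (Protocol 7.2.3); the 28-day safety visit has neither blood count nor marrow (7.2.4).
- EOT to first contact: 84 ± 7 = 77 to 91 days.
- Contact to contact: 84 ± 14 = 70 to 98 days.

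The shortest permitted gap, 70 days, is 14 over the limit. Every relapse first detected at a scheduled off-treatment visit is censored unless an unscheduled test fell within the preceding 56 days.

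**Deaths.** If death is equally likely on any day between two tested contacts L days apart, the share beyond day 56 is (L − 56)/L: 14/70 = 20%, 28/84 = 33%, 42/98 = 43%.

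**Share of relapses lost.** The documents do not say how many responders stop drug in remission or whether contacts include a test, so this part rests on assumptions. Simulation model: exponential time to relapse with median 120, 180 or 270 days; 10%, 25% or 50% stop in remission at a uniform time before relapse; 28-day detection on treatment; 730 days of follow-up.

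| Off-treatment pattern | 10% stop | 25% stop | 50% stop |
|---|---|---|---|
| A: test at each 12-week visit, relapse dated there | 10% | 25% | 50% |
| B: relapse dated by an interim local test, contacts restart the clock | 2% | 5–6% | 10–12% |
| C: telephone only, clock stays at EOT | 5–6% | 11–15% | 22–30% |

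Row A equals its input by construction, since every off-drug relapse is lost.

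**Kaplan-Meier median, 180-day relapse median.**
- A: 196 to between 196 and 224 days at 10% (it sits on the edge of a visit step), 196 to 252 at 25%, about 210 to 336 at 50%.
- B and C: within 4 days.

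The 4-day figure is specific to 180 days. At 50% stopping, a 120-day relapse median gives 129 to 140 for B and 129 to 114 for C; a 270-day median gives 280 to 308 for both.

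**Alternative exit model.** If all responders face an exponential time to stopping with median 180 days (relapse median 180), A loses 46% (median about 205 to 280), B 14% (about 193 to 196) and C 37% (about 194 to 168, downward).

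**Part 2 scale.** With an assumed OCRR of 20% to 40%, 20 × 0.2 = 4 to 20 × 0.4 = 8 responders. If 25% stop in remission, 1 to 2 patients are exposed.

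**The case against.** The strongest case concerns size. Protocol Table 1 shows only a telephone contact in survival follow-up, and 7.2.5 allows telephone or clinic and names no test. Protocol 4.3 asks sites to continue efficacy assessments in responders until recurrence, but gives no off-treatment frequency. Pattern A, which produces the largest upward shifts, is therefore an assumption about conduct. Under B and C the shift in the median can be small or go either way. Treatment is planned to continue until relapse, so few responders should leave it in remission. RFS is secondary and descriptive, and the SAP's patient listings (RFS, marrow, survival status, deaths) would let a careful reader find a censored event.

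All of this stands as a limit on size. It does not remove the mismatch: no permitted off-treatment gap fits within 56 days, and neither document makes an exception. Two escapes fail. The safety visit has no blood or marrow test, and even if it were counted, the later 84-day gaps would still exceed the limit. Interim tests do save some relapses, and deaths within 56 days still count, but the protocol requires no interim test after EOT. Telephone-only contact does not help either: the clock then stays at EOT, and every event more than 56 days later is lost.

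**Conclusion.** The concern holds. As written, the rule gives a wrong result for a stated secondary endpoint: fully compliant off-drug responders are censored as if they had missed visits. This follows from the planned intervals alone and needs no assumption about response or relapse rates.

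The practical size does need assumptions. Relapse losses run from 2% to 50% over the tabulated stopping rates and follow-up patterns. Upward bias is clear where off-treatment visits include a test and relapse is dated there; with telephone-only follow-up the direction is not fixed. About 1 to 2 Part 2 patients are exposed at 4 to 8 responders and 25% stopping in remission. With so few responders, one or two lost events could decide whether Kaplan-Meier is presented at all. Part 1 listings would also show real relapses as censored. OCRR is unaffected. This should be fixed, but it does not threaten the primary result.

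**What to change.** **Preferred.** In the main RFS analysis, count every relapse and every death from any cause as an event at its observed date, and move the 56-day rule to a sensitivity analysis. This matches Protocol 6.2, which runs RFS "until there is evidence of patient relapse or death from any cause (whichever happens first"), and the SAP's own inclusion of death. Protocol 3.3.2 and the synopsis omit death and should be aligned. This option also covers telephone-only follow-up. Its price is that some relapse dates will follow long untested gaps.

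**Alternative.** Tie the limit to the schedule in force:
- On treatment: 56 days, or 2 × 28 + 4 = 60 with windows.
- Off treatment: 2 × 84 + 14 = 182 days.

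The SAP should then say that two intervals mean one missed visit (154 to 182 days off treatment), that per-cycle hematology counts as an assessment, whether a telephone contact without a test counts, and which limit governs a gap that spans the end of treatment. With these limits, no compliant patient tested at every contact is censored. If an untested call does not count, telephone-only patients are still censored beyond day 182.

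**Cost.** Either option is SAP wording and programming before database lock, with no extra patients or procedures. Optionally, record at each 12-week contact the date and result of the latest routine blood count or marrow; that is new data collection, one added entry per contact.
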